Reporting: All adverse events will be compiled and reported in summary form on an annual basis to the AECOM-CCI, and at the conclusion of the study. Unanticipated (non-serious) adverse events will be reported to the AECOM-CCI within 30 days via submission of an Adverse Event Report. Serious adverse events will be reported to the AECOM-CCI within 48 hours by phone, email or fax. A completed Adverse Event Report will be submitted within 10 days of initial notification. All deaths will be reported to the AECOM-CCI within 48 hours.

E.8.g. Recruitment Monitoring:

Process: The DSMB chair will assess the recruitment and retention of study subjects on an ongoing basis. The recruitment goal for this protocol is 420 subjects.

Reporting: Summary statistics regarding recruitment and retention of study subjects will be reported to the AECOM-CCI on an annual basis, and at the conclusion of the study.

E.8.h. Early Study Termination:

Process: Due to the non-invasive nature of the protocol, it is not expected that early termination will be required due to adverse events. However, constant monitoring of the participants by members of the DSMB, [name], other investigators, and research staff will be maintained to ensure that adverse events are not occurring. Early study termination will occur in the event of any unanticipated serious adverse event determined to be possibly, probably or definitely related to study procedures, failure to recruit at least 50% of the projected number of subjects within 4 months, or failure to retain at least 75% of study subjects to the conclusion of the protocol.

Early stopping rules: An interim look for monitoring both efficacy and futility is proposed after approximately half the total numbers of subjects (n=210) are screened and finish post intervention assessments.

First, based on O'Brien-Fleming spending function,⁶ if the intervention group is significantly better than the control group at an alpha level of 0.003, the trial will stop early and conclude that the intervention group is significantly better. Since the O'Brien-Fleming stopping rule requires extreme evidence of efficacy at the midpoint of the trial, it does not inflate much the overall type I error rate.⁶ Therefore, with n=420 subjects total, our study still have more than 80% to detect a minimum detectable difference of 4 cm/s in velocity at an overall type I error rate of 5%. Second, we will compute the conditional power to determine if early stopping for futility is necessary.² The conditional power is defined as the probability of eventually rejecting the null hypothesis of no intervention effect given the current data and the data yet to be collected assuming the alternative hypothesis is true, specifically, a mean difference of 4 cm/s in gait velocity change (minimal detectable difference) between the intervention group and the control group. If the conditional power is below 10%, this trial will stop early for futility because there is little evidence of a beneficial intervention effect.²

Interim data reports:

The study statistician will prepare data reports and send them directly to the DSMB. The DSMB statistician will conduct the interim analyses. The interim analyses will be performed blinded to the study investigators. Based on the results from the interim analyses, the DSMB will recommend either early termination or continuation of the trial.

E.8.i. Reporting:

At the conclusion of each DSMB meeting, the Board will provide a verbal report to the PIs indicating areas of concern regarding performance and safety. The Board will take care not to convey any information that could lead to unblinding of the investigator. If the DSMB recommends a protocol modification, it must be approved by the NIA representative and the AECOM-CCI. If early termination is required, the DSMB Chair will report the decision to the AECOM-CCI within 48 hours of this determination, and submit a narrative description of the reasons for early termination within 10 days. The investigators will maintain a file of all adverse events that will be used to submit summary reports to the AECOM-CCI on an annual basis.

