C.8. Randomization. The Efron ('biased coin') procedure¹³⁹ will be used to assure near-equal sample sizes and good representation on three variables of interest (gender, age $<$ or $>$ 80 years, and NPW speed $<$ or $>$ 70 cm/s¹³⁷) in both groups. Also see C.15.e. It will not be efficient to randomize by more categories. Besides, variables such as illness are highly correlated with speed and age, and are dealt analytically as covariates. Group assignment will be dispensed in sealed opaque envelopes generated by [name] using sequential study numbers so that the assistant who enrolls the participants will be blinded to randomization assignment of the next participant until assigned. [name] will not be involved with subject testing or interventions.

C.9. Sample size. We will enroll **420 seniors (210 per group)**. Power and assumptions in section C.14.1.

[figure not shown]

Figure 3. Subject Flow

C.10. Blinding. Given the nature of our interventions, double-blinding both subjects and testers will not be feasible. But we will include a number of methods (besides randomization) to reduce bias.

- Selection bias will be reduced by concealing treatment allocation until the subject is entered into trial.¹⁴⁰
- Primary outcome is an objective endpoint (gait speed/SPPB) and not subjective mobility complaints.¹⁴⁰
- C-REM and health control interventions will be done in different sites and at non-overlapping times.
- The assessment team (and location) will be separate from intervention team.
- Participants and study staff will be instructed not to disclose group assignment or details of interventions.
- **Post-intervention questionnaire** (C.12.5) to assess maintenance of blinding.

C.11. Interventions. Both interventions will be given 3 times weekly for 8 weeks without crossover. C-REM program is supervised by [name] and the health education control by [name]. A **manual of operations** for all study activities will be developed during study setup (see **Table 3** in E.2.). Our intervention is based on a social cognitive model that views health behavior as being acquired and maintained through a complex set of behavioral, cognitive, and environmental conditions. Social cognitive theory concepts will be combined with strategies derived from applications of the Transtheoretical Model to mobility interventions^{59, 141} (e.g., consciousness raising early in the program; reinforcement management later in the program).^{59, 142}

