The sample size (420) provides >80% power to detect clinically meaningful differences at significance level of 0.05. The conservative Bonferroni correction for multiple testing was used in sample size calculations. Based on conservatively estimated SDs of 12 cm/s, 20 cm/s and 1.5 points for NPW, WWT and SPPB, respectively, to detect clinically meaningful differences of 5 cm/s for NPW and 0.5 points for SPPB with 80% power,^{10, 11} and a conservatively estimated 10 cm/s for WWT (16 cm/s WWT speed improvement in our pilot study¹³), at least 169 subjects per group are needed. To take account the projected 20% drop out rate at end of intervention, 210 subjects per group will be enrolled.

5 cm/s is the minimal detectable intervention change that we can study with 80% power, and is not the maximal threshold of change expected after C-REM in this RCT. Any improvement >5 cm/s by C-REM will increase power. For instance, we observed **8 cm/s** improvement in our pilot study²⁶ ('substantial improvement' range^{136, 193}), which will provide us >90% power to test our hypothesis in this RCT.

Durability: Assuming cumulative dropout rates of 25% at 6 months, with n=210 per group, we will have 92%, 99% and 75% power for detecting differences of 5cm/sec, 10 cm/s and 0.5 points in NPW, WWT and SPPB, respectively. At 1 year of follow-up, assuming 30% cumulative dropout, we will have 90%, 98% and 72% power

for detecting differences of 5 cm/sec, 10 cm/s and 0.5 points in NPW, WWT and SPPB, respectively. If the difference in SPPB is substantial (1 point), the power will be more than 95% at both time points. However, given the lower power to reliably estimate SPPB change, we designate the durability examination as an exploratory aim. We will seek additional funding to extend examination of durability.

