9. **Living in nursing home.**
10. **Participation in intervention trial.** Subjects can participate in other observational studies.

We acknowledge that we cannot control for all possible confounders, and that residual confounding can occur in all clinical trials. However, the randomization process in the clinical trial design will allow for equal allocation of potential confounders and effect modifiers between the two study groups.^{2,3}

E.2. Recruitment: To achieve our study aims aged adults will be recruited from a random sample of the Bronx and Westchester County residents, which is comprised of individuals age 70 and over who are in voter rolls by virtue of having voted in local or national elections in the past two years. We will also post flyers and advertisements at local clinics, stores, community centers and offices. We have had experience using this source to recruit over 1000 participants for various aging studies in the past 10 years including our pilot

intervention study. We will also identify potential participants age 70 and older who are patients at Montefiore through Clinical Looking Glass. The timeline for subject recruitment is shown in Table 3 below. The assumptions made in projecting the number of telephone screening interviews necessary to achieve the aims are based on experience in recruitment for the Einstein Aging Study as well as in our pilot study experience described in section B.5.c.^{1, 4, 5} Once telephone contact is achieved and the interview is complete, we assume that there will be a 20% loss due to lack of interest in the study and failure to meet general eligibility requirements and an additional 10% failure on the cognitive instrument (T-MIS). There is an additional 10% loss in the remaining sample due to failure to meet eligibility requirements. We will explore durability of effects up to 12 months follow-up. Due to study logistics and power considerations, durability will be examined as an exploratory sub-aim till month 57.

Table 3. Timetable and projected subject numbers at baseline and at post-intervention assessments.

Study set up	Year: 1 2 3 4 1 2 3 4 1 2 3 4 1 2 3 4 1 2 3 4												5							
	Quarters:	1	2	3	4	1	2	3	4	1	2	3		1	2	3	4	1	2	3
Screening	x	x	x	x	x	x	x	x	x	x	x	x		x	x	x	x	x	x	x
Intervention, n	26	26	26	26	26	26	26	26	26	26	26	26		26	26	26	28	28	26	
Post-intervention tests, n	21	21	21	21	21	21	21	21	21	21	21	21		21	21	21	23	23	21	

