6 month follow-up, n				15	15	15	15	15	15	15	15	15		15	15	15	15	15	15	
12 month follow-up, n				14	14	14	14	14	14	14	14	14		14	14	14	14	14	14	
Data cleaning/analysis																				
Interim analysis (DSMB)																	x (when 210 subjects complete intervention)			
Manuscript preparation																				

E.3. Sources for research material: Research material obtained from human subjects will be the results of clinical and neuropsychological testing obtained from study assessments and telephone interviews. The subject and their primary care physician will be informed of all clinical results that are relevant to patient care.

E.4. Potential risks: Answering health questionnaires and mental state examinations involve minimal psychological, social, or other risks. We do not expect any serious adverse events during these non-invasive tests and training programs of attention and executive function. The C-REM interventions involve mental but no physical effort by the participants. The health education control involves computer based health education. The fNIRS procedures utilize light in visible spectrum and do not pose any risk. Minimal discomfort may be experienced from local forehead pressure. Since there are no significant risks associated with the procedures, this study is justified because useful new scientific knowledge will be obtained.

E.5. Protection against risk: The research staff and investigators will be present during all testing. All questionnaire completion will be done at a slow enough pace so as not to tire individuals. If subjects express physical or mental tiredness or discomfort during any of the assessments or training procedures, the procedure will be terminated immediately. Drs. [name] or [name] will be available onsite or by pager at all times to address any safety concerns or clinical issues during the interventions.

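### Table 3 projects about 42% and 46% loss by 6 and 12 months, while the durability power and secondary detectable differences assume 25% and 30%

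*Combined protocol and SAP*

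**What the plan says.** **Planned size.** C.9 states: "We will enroll 420 seniors (210 per group"). C.13 and C.14.1.b allow for 20% loss by the end of the intervention.

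**Power section.** The durability paragraph of C.14.1.b begins "Assuming cumulative dropout rates of 25% at 6 months, with n=210 per group" and gives power of 92%, 99% and 75% for NPW, WWT and SPPB. For 1 year it takes 30% cumulative dropout and gives 90%, 98% and 72%. C.14.2.a uses the same two rates for the secondary outcomes and gives detectable differences of 0.29 and 0.30 SD.

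**Timetable.** Table 3 in E.2 is presented as the projected subject numbers at each assessment. Its intervention row shows 26 in most quarters and 28 in two. The row "Post-intervention tests, n" shows 21 (23 for the two larger entries). The row "6 month follow-up, n" shows 15 in every filled column, and the row "12 month follow-up, n" shows 14 in every filled column.

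No passage says that only a subset is followed after week 9, or otherwise accounts for the lower counts.

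**The concern.** The week-9 row of Table 3 agrees with the 20% loss in the text, so the table does build in attrition. The next two rows then depart from the power section by a wide margin: retention of 58% and 54% from entry, against 75% and 70%. Either the projected follow-up counts are too low, or the durability power and the secondary detectable differences rest on more people than the investigators expect to see.

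Two things are at stake. First, C.14.1.b gives low SPPB power as the reason for making durability exploratory; on Table 3's counts that weakness is greater than disclosed. Second, E.8.h names retention below 75% at the conclusion of the protocol as a ground for ending the study. Those monitoring retention therefore need one agreed projection to compare with, and at present they have two.

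**Working it through.** **Inputs**
- 210 per group (C.9).
- C.14.1.b: "Based on conservatively estimated SDs of 12 cm/s, 20 cm/s and 1.5 points for NPW, WWT and SPPB, respectively". Differences of 5 cm/s, 10 cm/s and 0.5 points.
- Alpha: C.14.1.b says "at significance level of 0.05" and "The conservative Bonferroni correction for multiple testing was used in sample size calculations". Neither the divisor nor the sidedness is given, so both are assumptions here.
- Table 3 entries: 26, 21, 15, 14; and 28, 23, 15, 14 for the two larger quarters.

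**Step 1. Loss implied by Table 3**
- Week 9: 1 − 21/26 = 19.2%, in line with the planned 20%.
- 6 months: 1 − 15/26 = 42.3%, against 25%.
- 12 months: 1 − 14/26 = 46.2%, against 30%.
- Entries of 28: 1 − 15/28 = 46.4% and 1 − 14/28 = 50.0%.

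**Step 2. Could damage to the extracted table explain this?** The rates in C.14.1.b imply 420 × 0.75 = 315 and 420 × 0.70 = 294 people assessed. At 15 and 14 per column, either row would need 315/15 = 294/14 = 21 filled columns. The timetable has 20 quarters. Sixteen columns, the number that gives exactly 420 entrants (14 × 26 + 2 × 28), would yield 240 and 224, or 57% and 53%. The 17 cycles of C.13 would yield 255 and 238, or 61% and 57%. None reaches 75% or 70%.

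**Step 3. Reproduce the stated power.** Normal approximation, equal groups:

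power = Φ( δ / (σ√(2/n)) − z₁₋α/₂ )

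with n = 210 × 0.75 = 157.5 and 210 × 0.70 = 147. Example, NPW at 6 months with alpha 0.025: 5/(12 × √(2/157.5)) = 3.698; 3.698 − 2.241 = 1.456; Φ = 92.7%.

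| Alpha (two-sided) | 6 months, NPW/WWT/SPPB | 12 months, NPW/WWT/SPPB |
|---|---|---|
| Stated in plan | 92/99/75% | 90/98/72% |
| 0.05 | 95.9/99.3/84.1% | 94.7/99.0/81.5% |
| 0.025 | 92.7/98.6/76.3% | 90.8/98.0/73.1% |
| 0.05/3 | 90.4/98.0/71.4% | 88.1/97.1/67.9% |

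Only 0.025 comes within 2 points of all six stated values. It is also the closest fit to the 169 per group quoted for week 9, where SPPB power is 79.5% at 0.025 and 74.9% at 0.05/3.

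**Step 4. Power at Table 3's retention.** The numbers per group are extrapolated: n = 210 × 15/26 = 121.2 and 210 × 14/26 = 113.1.

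| Alpha (two-sided) | 6 months, NPW/WWT/SPPB | 12 months, NPW/WWT/SPPB |
|---|---|---|
| 0.05 | 90/97/74% | 88/96/71% |
| 0.025 | 84/95/64% | 81/94/60% |
| 0.05/3 | 80/93/58% | 77/91/54% |

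Comparing the two tables at the same alpha, SPPB loses about 10 to 13 points, NPW about 6 to 11 and WWT about 2 to 6.

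**Step 5. Secondary detectable differences.** These scale with 1/√n, so the ratio does not depend on alpha: √(157.5/121.2) = √(147/113.1) = 1.14. I give only the ratio, because the same formula at 157.5 and 147 per group returns 0.32 and 0.33 SD at two-sided 0.05 and does not reproduce the stated 0.29 and 0.30.

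**The case against.** The strongest reply is that Table 3 is an administrative timetable and is badly preserved. As extracted, its 18 intervention entries sum to 472 instead of 420, the two follow-up rows start in the same column, and those rows stay at 15 and 14 even where 28 people entered. They might be scheduling figures and not tracked attrition. This is a good reason not to use row totals, and none are used above. It does not remove the mismatch: the cell values are uniform, the table is offered as projected subject numbers, and no feasible column count reaches 315 or 294.

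A second reply concerns weight, and it stands. Durability is called exploratory in the Specific Aims, C.14.1.b and E.2. At alpha 0.025, NPW and WWT stay above 80% at both visits even on Table 3's counts, and the plan already puts SPPB below 80%.

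Two stronger readings are tempting, and the documents support neither.
- A reader might infer that the trial's power is overstated throughout. It is not: 21/26 matches the planned 20% loss, so the week-9 comparison is unaffected.
- A reader might infer that 25% and 30% were applied on top of the 20% loss, since 21 × 0.75 = 15.75 and 21 × 0.70 = 14.7. That requires truncation, whereas the row above rounds up (28 × 0.8 = 22.4 appears as 23), which would give 16 and 15. Equally, 15 and 14 are exactly 75% and 70% of 20. The origin cannot be settled from the text.

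**Conclusion.** The inconsistency is real and limited in reach. Table 3's follow-up counts imply about 42% and 46% loss from entry; C.14.1.b and C.14.2.a assume 25% and 30%; nothing reconciles them. The documents do not show which is the true expectation.

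If it is Table 3, the durability power is overstated. The shortfall is modest for WWT, moderate for NPW and largest for SPPB, which falls to roughly 64% and 60% at alpha 0.025. The secondary detectable differences at 6 and 12 months would be about 14% wider. If it is C.14.1.b, the power figures stand and only the table is wrong.

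These sizes assume a two-sided test, an alpha inferred from the plan's own powers (range shown for 0.05 to 0.05/3), the planned SDs, and Table 3's 26-entrant proportions applied to 210 per group. The primary analysis and the sample size do not change.

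**What to change.** Adopt one attrition schedule and use it in C.14.1.b, C.14.2.a and Table 3, and as the reference when retention is reviewed under E.8.h. There are two options:

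- **Keep 25% and 30%.** Correct the follow-up rows of Table 3 to about 19-20 (26 × 0.75 = 19.5) and 18 (26 × 0.70 = 18.2) per 26 entrants, with the 28-person entries scaled to match (21 and 19.6).
- **Keep Table 3.** Restate the dropout rates as about 42% and 46%, and recompute the durability power and the C.14.2.a detectable differences at about 121 and 113 per group.

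In either case, state the alpha, sidedness and Bonferroni divisor behind the power figures so that they can be checked. The cost is restating figures; no design, enrolment or primary analysis change follows.

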E.7. Importance of the knowledge to be gained: The information that is expected to result from these studies should be of importance for understanding the biology, better diagnosing, and treating mobility disability in the aged. The results expected from this project should improve the treatment of mobility and provide information needed for rehabilitation of mobility disability.

E.8. DATA AND SAFETY MONITORING PLAN.

E.8.a. Introduction: All data collection in this clinical trial will be monitored to assure subject comfort, safety, and confidentiality. The clinical trial protocols, data collection instruments, subject recruitment letters, and consent forms will be reviewed and approved by the **Albert Einstein College of Medicine Committee for Clinical Investigations (AECOM-CCI)**. The AECOM-CCI will also approve the creation and structure of the Data and Safety Monitoring Plan.

E.8.b. Membership:

The Data and Safety Monitoring Board (DSMB) will be appointed in consultation with the responsible program official at NIA and in line with federal and IRB guidelines if the study is funded.

E.8.c. Safety Monitoring:

Prior to beginning data collections, [name] and the DSMB Chair will reconfirm that our site has appropriate safety measures in place. The DSMB will meet with the entire research team to review the study protocols. Particular attention will be paid to outcome definition, study design, procedures for recording and reporting adverse events, and informed consent procedures and documentation.

At the initial meeting, the DSMB may recommend modifications or clarification of the protocol, and it will formulate its operating procedures (e.g., meeting schedule, reports due dates for the study statistician, unblinding policy, and what interim data may be released to the investigators). At the initial meeting the plans for interim monitoring for efficacy and futility will be presented to the DSMB as an aid for monitoring the trial (see E.8.h. below).

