We will train competent staff to conduct the interventions and assessments, ensure they understand the nature of the interventions, and understand adverse event reporting requirements. Trained clinical assistants, who will monitor the subject for any adverse events, will perform all assessments. We do not expect any serious adverse events during these non-invasive interventions. The clinical assistant will stop the testing procedures if subjects feel stressed or get embarrassed by their performance, and relay the information immediately to [name], [name], or [name]. At least one investigator will be present onsite during all testing and intervention sessions. In addition Drs. [name] and [name] will be available by pager and cellular telephone at all times to address any safety concerns or clinical issues.

E.8.d. Data Monitoring:

Participant confidentiality will be maintained by assigning each subject a unique study ID upon entry to identify and link subject data. ID and name associations will be password protected in an encrypted master file to which only the data manager and PIs have access. Further protection for confidentiality is assured in that we will avoid telnet or FTP remote access. For added security, database copies will be kept in two separate physical locations in locked, fire-resistant containers. Also see E.5.

E.8.e. Interim meetings:

Both closed and open meetings of the DSMB will be held at six-month intervals. In addition the DSMB will meet more frequently as study progress dictates. The study statistician will prepare databases to be sent to the DSMB statistician for the closed session at least 7 days prior to the meeting. The DSMB statistician will bring reports for the closed session to that meeting. She will collect all copies of these reports at the conclusion of the closed session to ensure that study investigators remain blinded to the interim results.

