The open session report will focus on patient accrual and demographics, data completeness, and other study performance measures. Only aggregate data will be presented during the open session (i.e., not segregated by treatment). The closed session report will divide study participants according to coded treatment assignment (C-REM or health education control), comparing participant demographics and baseline characteristics, rates and reasons for treatment discontinuation and loss to follow-up, and rates of serious adverse events. The interim efficacy analysis will be included only in the report for the closed session. In addition to reports prepared by the statistician, the Principal Investigators may prepare a report addressing concerns he anticipates the DSMB will have regarding the conduct of the study.

The interim data reports will include:

- Monthly and cumulative accrual
- Baseline characteristics, overall and by treatment group
- Summary of completeness and quality of data collection forms
- Status of enrolled patients, overall and by treatment group
- Assessments of whether study personnel have followed eligibility criteria and other protocol requirements
- Assessment of participant adherence, overall and by treatment group
- Sample size assumptions
- Outcome rates, overall and by treatment group along with monitoring boundaries for efficacy and futility (if the planned interim look is due)
- Listing of serious adverse events by participant ID number and a table of event-specific cumulative rates, overall and by treatment group
- A summary description of all serious adverse events

Only the closed session report will include the comparisons by treatment group.

E.8.f. Adverse Event Monitoring:

Process: DSMB chair, to be named, will perform data and safety monitoring on an ongoing basis. She/he will not be otherwise involved in assessments or interventions in this clinical trial. The PIs or research staff will see all volunteers. All abnormal findings from the clinical, mobility, and neuropsychological assessments done on Day 1 will be documented on a case report form and reviewed by the DSMB chair. Periodic audits from the AECOM-CCI ensure compliance with confidentiality guidelines and adverse events monitoring.

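### E.8.h ends the whole trial after one unanticipated serious adverse event rated at least possibly related to study procedures, with no review step in the clause; a pause plus DSMB review would be a cheap improvement

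*Combined protocol and SAP*

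**What the plan says.** The safety trigger is in the first paragraph of E.8.h: "Early study termination will occur in the event of any unanticipated serious adverse event determined to be possibly, probably or definitely related to study procedures". The same sentence goes on to list poor recruitment and poor retention as further triggers. The section heading shows that the whole study is meant, not one participant's involvement. The clause does not distinguish between arms, and 'study procedures' covers the testing as well as the sessions.

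The interim look is set out next in E.8.h. Its efficacy and futility rules are also phrased as firm stops. The paragraph on interim data reports then adds: "Based on the results from the interim analyses, the DSMB will recommend either early termination or continuation of the trial".

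The DSMB's general role is spread over E.8.c to E.8.i:

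- E.8.c, on the initial meeting: "the DSMB may recommend modifications or clarification of the protocol, and it will formulate its operating procedures".
- E.8.e: "In addition the DSMB will meet more frequently as study progress dictates".
- E.8.f: "DSMB chair, to be named, will perform data and safety monitoring on an ongoing basis".
- E.8.f, on reporting to the institutional review board (IRB): "Serious adverse events will be reported to the AECOM-CCI within 48 hours by phone, email or fax".
- E.8.i: "If early termination is required, the DSMB Chair will report the decision to the AECOM-CCI within 48 hours of this determination".
- E.8.i also lets the investigators raise safety issues through the NIA representative, who consults the DSMB Chair about a special meeting.

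**The concern.** A stopping rule that fires on one event rated only possibly related leaves no room to ask whether the event says anything about the safety of C-REM or of the tests. A fall with fracture during a walking test, or a cardiac event at a visit, could end the trial even if it occurred in the control arm.

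Such an event is plausible in this population. Participants are 70 or older with an SPPB score of 9 or less (C.7). They walk at their fastest speed (C.12.1.a) and have stair climbing timed (C.12.4.e). E.1 does not exclude people with a recent heart attack, coronary procedure or stroke who otherwise qualify, although the six-month hospitalisation exclusion in C.7 would remove some of them.

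The word 'unanticipated' may not narrow the trigger much, because the plan anticipates almost nothing. E.8.c says "We do not expect any serious adverse events during these non-invasive interventions", E.4 says much the same, and E.6 says there are no risks.

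At stake is the loss of the trial, or a deviation from an approved stopping rule if staff decline to apply it literally.

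**Working it through.** The plan states no figure for this rule, so there is none to reproduce. The check has two parts.

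**1. Does any text make this stop conditional?**

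| Provision | What it does | Gates the serious-event stop? |
|---|---|---|
| E.8.h, safety trigger | Termination follows any one qualifying event | No condition beyond the relatedness rating |
| E.8.h, interim look | Firm stops, then a DSMB recommendation based on the interim analyses | No; tied to the interim analyses |
| E.8.c | DSMB may recommend protocol changes and sets its procedures | No; those procedures are not among the documents |
| E.8.e | Extra DSMB meetings possible | No; not tied to the trigger |
| E.8.f | Chair monitors safety; IRB told within 48 hours | No; oversight and reporting |
| E.8.i, termination | Chair reports the decision if termination is required | No; a reporting duty, though it implies a DSMB role |
| E.8.i, investigators | Special meeting may be considered | No; not tied to the trigger |

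Once someone rates the event possibly related, the clause leaves nothing further to decide.

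**2. Over how much exposure is no event tolerated?**

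Inputs: 420 participants (C.9); 24 sessions each in both arms (C.11.3, Table 2); dropout of 20% at the end of intervention, 25% at 6 months and 30% at 12 months (C.14.1.b).

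- Sessions, upper: 420 × 24 = 10,080.
- Sessions, lower, if the 20% who drop out attend none: 420 × 0.80 × 24 = 8,064.
- Mobility-test visits (baseline, week 9, 6 and 12 months): 420 × (1 + 0.80 + 0.75 + 0.70) = 1,365.
- Contacts: 8,064 + 1,365 = 9,429 to 10,080 + 1,365 = 11,445.

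Most of these contacts are seated computer sessions. The physically demanding ones are the roughly 1,365 test visits.

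**Illustration only.** The documents give no event rate. If each participant had an assumed probability q of a qualifying event, independently of the others, the chance that the rule fires would be 1 − (1 − q)^420:

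| Assumed q | Chance of firing |
|---|---|
| 0.01% | 4% |
| 0.05% | 19% |
| 0.1% | 34% |

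Conversely, a 10% chance needs q = 1 − 0.9^(1/420) = 0.000251, about 1 in 4,000 participants. Counted per test visit, it needs 1 − 0.9^(1/1365) = 0.0000772, about 1 in 13,000 visits. These rates are assumed and carry no weight in the grading.

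**The case against.** The strongest reply is that the clause is not self-executing. The interim rules in the same section are just as firm in wording and yet coexist with a DSMB recommendation. E.8.i speaks of a decision and a determination reported by the DSMB Chair, and it is not confined to the interim look. The trigger itself requires that relatedness be determined, which is a judgement. The retention limb of the same sentence points the same way: it demands 75% retention to the end of the protocol, while C.14.1.b assumes 30% dropout at 12 months. If the end means 12 months, a literal reading has the plan expecting its own termination. On this view the sentence lists grounds for stopping, and all that is missing is a cross-reference.

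Much of this stands. A DSMB role is implied, and the contrast with the interim look is one of an added recommendation, not of firm against soft wording. It does not remove the point, because the safety clause has no such recommendation and no other text supplies one.

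The plan also has safeguards that make a trigger less likely. E.1 excludes any condition that the screening clinician judges would compromise safety. E.5 stops a procedure at once if the participant reports tiredness or discomfort. E.8.c keeps an investigator onsite for all testing and sessions. These stand too, and they are one reason why no probability can be attached to the trigger.

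Finally, zero tolerance can be defended as a cautious choice where E.6 promises participants little direct benefit. That supports an immediate protective step, which a pause provides. It does not require irreversible closure before anyone has reviewed the event.

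**Conclusion.** The point holds as a cheap improvement of low to moderate severity. It rests on the wording of E.8.h: one qualifying event, in either arm, at the lowest qualifying rating, with no review step in the clause.

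A reader might infer more than the documents support:

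- **That the DSMB is shut out of the decision.** It is not; E.8.f and E.8.i imply its involvement. The gap is that the stop is not made conditional on its judgement.
- **That the trial is likely to be stopped by this rule.** No event rate is given, so the chance is unknown.
- **That 'unanticipated' filters nothing.** The statements in E.4 and E.8.c concern the non-invasive tests, training and interventions, and do not mention falls during mobility testing. The consent form's risk list is not in the available text. E.6's broader statement makes weak filtering likely, not certain.
- **That the result would be distorted.** The rule does not bias the treatment estimate or inflate type I error.
- **That the unnamed assessor of relatedness is a separate error.** It is a detail to clarify, and the fix below does so.

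**What to change.** Replace the serious-event clause in E.8.h with wording such as:

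> If an unanticipated serious adverse event is thought at least possibly related to a study procedure, that procedure is paused immediately, and enrolment is paused at the DSMB Chair's discretion. The DSMB holds a prompt unscheduled review, confirms relatedness, and recommends that the trial continue, be modified or be terminated.

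Keep the 48-hour IRB reporting in E.8.f unchanged. If the DSMB's operating procedures already set out such a path, E.8.h can refer to them.

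The cost is one clause. If the DSMB recommends the change, E.8.i requires approval by the NIA representative and the IRB. It adds no participants, visits or staff. The downside is that a full stop no longer follows at once from a single event. The automatic pause limits that, and the DSMB keeps full power to recommend termination.
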